8.3.9 EVENTS OF SPECIAL INTEREST

Not-applicable.

8.3.10 REPORTING OF PREGNANCY

Not-applicable.

8.4 UNANTICIPATED PROBLEMS

8.4.1 DEFINITION OF UNANTICIPATED PROBLEMS (UP)

An Unanticipated Problem (UP) is any event, incident, experience, or outcome that meets the following criteria:

- Unexpected in terms of nature, severity, or frequency given (a) the research procedures that are described in the protocol-related documents, such as the IRB-approved research protocol and informed consent document; and (b) the characteristics of the participant population being studied;
- Related to participation in the research (meaning there is a reasonable possibility that the incident, experience, or outcome may have been caused by the procedures involved in the research); and
- Suggests that the research places participants or others at a greater risk of harm (including physical, psychological, economic, or social harm) than was previously known or recognized.

8.4.2 UNANTICIPATED PROBLEM REPORTING

All unanticipated problems will be collected and defined as per the Unanticipated Problems Involving Risks & Adverse Events Guidance (2007) – HHS regulations at 46.103(b)(5).

To satisfy the requirement for prompt reporting, UP will be reported using the following timeline:

- UPs that are SAEs will be reported to the sIRB, local IRB, and the SAC within 24 hours of the investigator becoming aware of the event per the SAE reporting process described above.
- Any other UP will be reported to the sIRB, local IRB, and the SAC within 3 days of the investigator becoming aware of the problem.

As per the FDA guidelines [21 CFR 312.32(c)(2)], any unexpected fatal or life-threatening suspected adverse reactions to study active agent will be reported to the sIRB, local IRB, FDA, and DSMB no later than 7 calendar days after initial receipt of the information.

8.4.3 REPORTING UNANTICIPATED PROBLEMS TO PARTICIPANTS

Not-applicable.

9 STATISTICAL CONSIDERATIONS

9.1 STATISTICAL HYPOTHESES

The primary analysis will perform a two-sided $\alpha = 0.05$ test of the null hypothesis of no difference in mean whole blood NAD+ level changes from the baseline and day 10 between the two arms, versus the alternative that participants randomized to the intervention arm have a different mean change than those randomized to placebo..

9.2 SAMPLE SIZE DETERMINATION

We evaluated using a marker of efficacy for NR with the whole blood NAD+ based on two recent publications [8, 15]. In a study of healthy overweight subjects 40-60 years of age, Conze et al. [8] found a 21 µg/ml mean NAD+ difference between patients randomized to 1000 mg NIAGEN versus those randomized to placebo at day 7 (NIAGEN 42 µg/ml, Placebo 21 µg/ml) with a standard deviation of 10 µg/ml and approximately equal baseline means (NIAGEN 21 µg/ml). Simic et al. [15] assessed a combination of NR with pterostilbene (NRPT) vs placebo in hospitalized patients of age \geq 18 years with AKI and found an 18% increase in whole blood NAD+ within 48h post treatment in the NRPT group, and a 50% reduction from baseline in the placebo group with AKI. With reference to Conze et al. [8] al., this study will achieve >99.9% power for testing H₀:R_{NR} = R_{Placebo} versus H₀: R_{NR} ≠R_{Placebo} with alpha=0.05, autocorrelation (ρ)=0.5, and n=40 per arm where R_{NR} and R_{Placebo} are the rates of change from baseline to day 10 in the NR and Placebo arms, if the effects observed in this study are the same as those observed by Conze et al. with regard to NAD+. In this setting the effect size is 2.1 [=(42-21)/10] and the minimally detectable effect size is 0.63.

9.3 POPULATIONS FOR ANALYSES

We will summarize the number of participants that are screened, enrolled, and randomized, including reasons for exclusion at each step. In accordance with the intention-to-treat principle, the primary analytic population will consist of all randomized participants, who will be evaluated according to their randomly assigned treatment arm and regardless of whether they adhere to study protocol or complete the study. We will further analyze the safety population of all randomized participants who receive any amount of study drug, analyzed according to the study drug received rather than the assigned intervention.

9.4 STATISTICAL ANALYSES

9.4.1 GENERAL APPROACH

In general, continuously distributed data will be summarized with the sample size, mean, standard deviation, median, minimum, and maximum. Categorical and binary data will be summarized with frequencies and percentages. Raw data storage, documentation, and security will be effectively served with the REDCap platform. Participants will be randomized to treatments in randomly permuted blocks of size 2 and 4 stratified by clinical site.

The number of participants screened, the number of screen failures by reason, and the number eligible for randomization, the number randomized, and, by treatment (Placebo, NR), the number withdrawing from the study for any reason, lost to follow-up by reason, unable to receive at least one dose and replaced, and the number completing the study per protocol will be tabulated and summarized with a CONSORT Diagram. We will also describe adherence to treatment over the course of the study, overall and by treatment arm.

Randomized controlled trials often suffer from two major complications, i.e., noncompliance and missing outcomes. One potential solution to this problem is a statistical concept called intention-to-treat (ITT) analysis, to be used in this trial. ITT analysis includes every subject who is randomized according to randomized treatment assignment. It ignores noncompliance, protocol deviations, withdrawal, and anything that happens after randomization. ITT analysis maintains prognostic balance generated from the original random treatment allocation. In ITT analysis, estimate of treatment effect is generally conservative [83].

Missing data can threaten the inferences made about study questions. The study team will make every effort to minimize the impact of missing data, including attempting to obtain final information on participants even if adherence to study procedures is poor or they do not follow the randomized treatment. In cases where missing data is unavoidable, we will use multiple imputation using chained equations to impute outcomes and relevant covariates to mitigate the potential impact of missing data, combining across imputations with Rubin's rules to account for the variability in the imputation procedure [84]. Any data point that appears erroneous or inexplicable based on clinical judgement will be investigated by study staff. If data points are considered to be outliers then sensitivity analyses will be carried out with and without the suspected outlier. Under the missing at random (MAR) assumption the estimates provided by our planned repeated measures statistical models using maximum likelihood estimation will be asymptotically unbiased [85].

All data will be summarized by treatment and clinical site in all randomized participants. Statistical estimates of treatment effects (with 95% confidence intervals, where appropriate), and p-values will be tabulated. All statistical tests will be two-sided with a significance level of 5%. R and/or SAS will be used throughout. Due to the overall exploratory nature of this study corrections for multiple comparisons will not be applied.

9.4.2 ANALYSIS OF THE PRIMARY EFFICACY ENDPOINT(S)

PRIMARY END POINT: Blood NAD+ level

The null hypothesis to be tested is H₀:R_{NR}=R_{Placebo}, where R_{NR} and R_{Placebo} are the rates of change from baseline to day 10 in the NR and Placebo arms. We expect that the rate of change in NAD+ from baseline to day10 with NR treatment will be increased relative to Placebo. Whole blood NAD+ will be measured daily in each patient during the first 10 days upon randomization. NAD+ level changes from the baseline will be graphically summarized with overlaid line and whisker plots of the mean trajectory for each arm with the whiskers being of length equal to one standard error of the mean. The significance of treatmement group differences with regard to the rate of change of NAD+ will be assessed using the methods of Schluchter et al [86] to address informative censoring, due for example to dialysis and death, with a random subject effect to account for the correlation among repeated measures within an individual. The model will include treatment and day. The day by treatment interaction will be of interest and will be addressed with the coefficient of the day by treatment interaction term to be added to the unadjusted model. Adjusted analyses will be carried out with age, race, clinical site, baseline serum creatinine, treatment and day included in the model. The unadjusted and adjusted models will be summarized with the coefficients, standard errors, 95% confidence intervals and pvalues. A day by treatment interaction term, treatment by day, and treatment by clinical site interactions will be considered and reported and described if found significant (p < 0.10). We will examine potential treatment interactions among subgroups of interest such as age, and sex. Consistent with the power calculation (Section 9.2), these models will be used to provide treatment group contrasts on the mean rate of change (estimated by the coefficient of day in the model, also known as the slope parameter), summarized with the model-based mean rates of changs, mean differences in rates of change and 95% confidence intervals and p-values. Spaghetti plots and plots of the mean NAD+ trajectories by treatment group, and mean rates of change, will be reported.

Potential participants who may have severe AKI or advanced CKD will be considered with a binary independent variable in the models addressing this condition with corresponding displays of the line and whisker plots by treatment group and summary tables of coefficients, standard errors and p-values. Interactions between this binary variable and treatment will be of interest and will be described.

Capture and tabulation of concomitant medications, dialysis, co-enrollment in another COVID-19 clinical trial, any new standard of care, pre-existing CKD, and treatments by study arm (NR, Placebo) may be used to define other potential adjustments with binary or categorical variables to be defined post hoc in exploratory analyses. Such models may motivate extended interpretations of any treatment effects found.

PRIMARY END POINT: Safety

All reportable AEs will be listed by Preferred Term by subject, treatment, clinical site, grade, relation to treatment, severity, and seriousness. All unanticipated events will be listed by treatment and clinical site with a detailed description of each event, incident, experience or outcome. An unblinded statistician will summarize safety data periodically for the DSMB.

AEs will be tabulated by treatment and clinical site, displaying, for each event, the number and percentage of participants experiencing at least one Grade 3 or 4 occurrence and he null hypothesis to be tested is H_0 : $p_{NR}=p_{Placebo}$ where p_{NR} and $p_{Placebo}$ are the probabilities of experiencing at least one Grade 3 or Grade 3 event in the NR and Placebo groups. H_0 will be tested with Fisher's Exact test, overall and by clinical site. Additionally, treatment groups will be contrasted on the occurrence at least once of each event with Fisher's exact test. All statistical testing will be two-sided with a significance level of 5%.

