8.2 SAFETY AND OTHER ASSESSMENTS

Assuring participant safety is an essential component of this protocol. NR is considered GRAS (Generally Recognized as Safe) as filed for designation to FDA. Use of NR for the prevention and or treatment of AKI in COVID-19 positive participants, however, raises unique safety considerations. This protocol addresses these considerations through:

- Exclusion criteria designed to prevent potential overdose effects by excluding participants with concomitant intakes of niacin, nicotinamide, and NR;
- Daily assessment of participants health status;
- Systematic collection of safety outcomes;
- Structured reporting of adverse events;
- Appointment of independent safety adjudication committee (SAC)

Study procedures and evaluations to be done as part of the study to monitor safety and support the understanding of the study intervention's safety. For all visits starting from baseline until the last follow-up visits, the following assessments will be completed:

- Physical examination: A physical examination at the baseline visit or a record of routine physical examination performed within 24 hours prior to consenting, and at Day 30, and Day 90 follow-up visits.
- During the 10-day intervention period, participant's health status will be obtained on a daily basis from the participant and from EHR. Health status of participants will be collected by the study team at Day 30, and Day 90 follow-up visits. Participants will be specifically asked for any new symptoms on a daily basis.
- The safety clinical laboratory parameters will be performed at each visit while hospitalized. Any laboratory tests performed as part of routine clinical care (Clinical Laboratory Tests) within the specified visit window will be used for safety laboratory testing (see Table 4).

Research laboratory tests:

Blood for the first whole blood NAD+ level will be drawn within 6 hours prior to the first study drug dosing (i.e., baseline NAD+ level, Day 1). Whole blood NAD+ level will be measured daily for a total of 10 days while hospitalized starting at the baseline.

Safety laboratory from routine daily laboratory tests:

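### The primary NAD+ model leaves baseline NAD+ unused: a modest loss of efficiency, not a bias, that a small change of wording can recover

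*Combined protocol and SAP*

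**What the plan says.** Section 9.4.2 tests whether the rate of change in whole blood NAD+ from baseline to Day 10 differs between arms. It uses a cited informative-censoring method with a random subject effect. For the fixed effects, "The model will include treatment and day", and the day-by-treatment term is added to that unadjusted model. For the second version, "Adjusted analyses will be carried out with age, race, clinical site, baseline serum creatinine" are listed with treatment and day. The further and post hoc adjustments described after that (severe AKI or advanced CKD, concomitant medication, co-enrolment and so on) do not include baseline NAD+.

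The baseline value exists. Section 8.2 states: "Blood for the first whole blood NAD+ level will be drawn within 6 hours prior to the first study drug dosing". Allocation is 1:1 (Section 6.1.1).

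Section 9.2 supplies the planning figures. The design is set "with alpha=0.05, autocorrelation (ρ)=0.5, and n=40 per arm", the literature value comes "with a standard deviation of 10" µg/ml, and the stated result is: "In this setting the effect size is 2.1 [=(42-21)/10] and the minimally detectable effect size is 0.63".

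**The concern.** With a treatment main effect in the model, each arm gets its own fitted Day 1 mean. The trial then spends information estimating a baseline difference that randomisation has already made zero in expectation. With only baseline and Day 10, the slope contrast is simply the difference in change scores. Given an observed baseline imbalance, that contrast moves by -(1 - rho) per unit of imbalance, which is half the imbalance at rho = 0.5. With ten daily values the effect is milder: lasting differences between participants cancel from a random-intercept slope, and only the Day 1 residual enters, with weight 4.5 × 9/82.5 = 0.49 on the 9-day scale.

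At stake is the width of the interval for the pilot's main estimate. Significance on NAD+ drives two of the three go-forward scenarios in Section 2.1. The plan also adjusts for baseline creatinine but not for the outcome's own baseline, without giving a reason.

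**Working it through.** **Inputs.** n = 40 per arm, rho = 0.5, alpha = 0.05, SD 10 µg/ml, effect size 2.1 and detectable effect 0.63 (Section 9.2); two-sided tests (Section 9.4.1). Section 5.5 gives 100 randomised, with 15% withdrawal and 5% further attrition: 100 × 0.80 = 80, or 40 per arm. Assumed, because not stated: 80% power behind the 0.63, and the random subject effect read as a random intercept (exchangeable correlation).

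**Reproducing the plan's figures.** SD of the baseline-to-Day-10 change = 10 × √(2(1 - 0.5)) = 10. Detectable effect = (1.960 + 0.842) × √(2/40) = 0.626, or 0.634 with the t distribution, which matches 0.63. At 90% power it would be 0.72. Power at 2.1 exceeds 99.9%. Reading rho as day-to-day AR(1) gives 0.89 (two points) or 0.82 (ten-day slope), so it does not reproduce 0.63.

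**Baseline-to-Day-10 change** (units of SD²):
- Separate baseline means: (2/n) × 2(1 - rho) = 0.05 × 1 = 0.0500.
- Common baseline mean, or baseline as covariate: (2/n) × (1 - rho²) = 0.05 × 0.75 = 0.0375.
- Variance ratio (1 + rho)/2 = 0.75; SE ratio 0.866; detectable effect 0.626 to 0.543.
- Power at 0.63 rises from 80.4% to 90.2%. The number needed for 80% power falls from 40 to 30 per arm.

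**Ten daily values, random intercept, difference over 9 days.** Let t = 0, …, 9, so the sum of t is 45, the sum of t² is 285, and the sum of squares about the mean is 82.5.
- Separate baseline means: 81 × 2(1 - rho)/(n × 82.5) = 81/(40 × 82.5) = 0.0245.
- Common baseline mean: 81 × 2/(n × K), where K = [285 - rho × 45²/(1 + 9 rho)]/(1 - rho) = 2 × (285 - 184.09) = 201.8. This gives 162/(40 × 201.8) = 0.0201.
- Variance ratio 0.818; SE ratio 0.904; detectable effect 0.44 to 0.40.

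**How the variance reduction moves with the assumptions:**

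| Setting | Variance reduction |
|---|---|
| Baseline to Day 10, rho 0.3 / 0.5 / 0.7 | 35% / 25% / 15% |
| Ten daily values, random intercept, rho 0.3 / 0.5 / 0.7 / 0.8 | 32% / 18% / 9% / 6% |
| Days 1-5 and 10 only (early discharge), rho 0.5 | about 14% |
| Random slopes added (assumed variances) | about 1% to 24% |
| Ten daily values, AR(1) at 0.5 | about 63%, but this reading does not reproduce 0.63 |

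**Does the form of adjustment matter?** Yes.
- Fitting a slope to Days 2-10 with a free treatment term and baseline NAD+ as a main-effect covariate removes Day 1 from the slope. The sum of squares falls from 82.5 to 60, so slope variance becomes 82.5/60 = 1.375 times the planned one.
- A common baseline with linear day changes the estimate if the arm difference is not linear. Suppose the difference is fully present from Day 2 and then flat. The planned model gives 9 × 4.5/82.5 = 0.49 of the plateau. The constrained model gives 9 × 2 × (45 - 0.5 × 45 × 9/5.5)/201.8 = 0.73. If the difference rises linearly to Day 7 and then stays flat, the values are 1.08 and 1.12.

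**The case against.** The strongest reply is that nothing here is wrong. A slope comparison with separate intercepts is standard and unbiased, the study is an exploratory pilot, and Section 9.2 says "this study will achieve >99.9% power for testing" the planned effect. Power at 2.1 stays above 99.9% with or without the change, so the gain matters only if the true effect is far smaller, near 0.63 or below. That stands, and it limits how hard the point can be pressed. What remains is that the 2.1 comes from healthy overweight volunteers, whereas this trial enrols hospitalised patients with COVID-19 and AKI, and the interval is itself a main product of a pilot.

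A second reply is that complete daily data will not exist. Section 8.2 has NAD+ measured daily only during hospitalisation, and discharged participants give research blood only on Day 10 (Section 8.1). This also stands, and it lowers the slope gain to about 14% in the pattern tried.

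A third reply is that the constraint is not neutral. Sections 2.3.1 and 9.2 cite an effect within 48 hours, and Section 4.3 cites peak levels at 7 and 14 days, so a linear arm difference is doubtful. This stands too, and it shapes the remedy. The test remains valid under the null, because with no arm difference on any day the constrained slope difference is also zero in expectation.

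**Conclusion.** The omission is confirmed, and its cost is moderate and conditional. At rho = 0.5 with 40 per arm, it gives up about 18% of the variance for the planned slope (random intercept, complete daily data) and 25% for the baseline-to-Day-10 change in which Section 9.1 words its hypothesis. On the standard-error scale this is about 10% to 13%.

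The documents do not support three stronger readings that a reader might infer:
- *That the treatment estimate is biased.* Randomisation equalises the baseline means in expectation, so only efficiency is lost.
- *That a fifth to a quarter of precision is lost whatever the data look like.* The slope figure is already below a fifth at rho = 0.5. It falls further with higher correlation, early discharge and, in most settings tried, random slopes.
- *That the trial is underpowered for its stated effect.* It is not.

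This is a cheap improvement rather than a defect that must be repaired.

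**What to change.** In Section 9.4.2, code day as 0 at baseline and constrain the arms to a common baseline mean, so that treatment enters the primary model only through day-by-treatment.

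Because NAD+ may rise early and plateau, also report the Day 10 contrast, either adjusted for baseline NAD+ or from a common-baseline model with day as categorical. Either gives the 25% variance reduction at rho = 0.5, relative to the simple change, without assuming linearity.

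Do not use baseline NAD+ merely as a main-effect covariate in a Days 2-10 slope model with a free treatment term, since that raises slope variance about 1.375-fold.

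The cost is a few lines of wording, fixed before unblinding, with no extra samples, visits or participants. The small downside is that the constrained linear slope gives a different estimate if the arm difference is not linear in time. The plan should say so and name which contrast is primary.

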The null hypothesis to be tested is H_o : $R_{NR}=R_{Placebo}$, where R_{NR} and $R_{Placebo}$ are the mean rates of change of eGFR in patients randomized to NR or to Placebo respectively from baseline to day 30 and day 90. We expect the eGFR rate of change to be increased with NR relative to Placebo. The same hypothesis will be tested for proteinuria, using log-transformed urinary albumin-to-creatinine ratio, where we expect the mean proteinuria rate of change to be decreased with NR relative to Placebo.

We will quantify kidney dysfunction at 30 days and 90 days post-randomization, measured by eGFR calculated by the CKD-EPI (the Chronic Kidney Disease Epidemiology Collaboration) equation [87] and the urine protein/creatinine ratio (PCR). To address non-ignorable missingness due to dialysis, death, or withdrawal of consent, all of which may be considered as informative censoring, the statistical method will be the same as that specified for NAD+.

eGFR will be evaluated untransformed, while urine PCR will be log-transformed to evaluate percent change because urine PCR is highly skewed and relative changes in urine PCR are proportional to risk of adverse renal and cardiovascular outcomes. We will include time, treatment, and interactions of treatment with time as independent variables in a mixed effects linear model. We will focus on the coefficient for the interaction of treatment with time as the primary measure of treatment effect. We will consider a p-value <0.05 for this interaction term to indicate a significant treatment effect. These analyses will be further adjusted for baseline characteristics that are prognostic of the outcome, including age, sex, clinical site, and stage of AKI at randomization. Adjustment will be accomplished by adding covariates and interactions of covariates with time.

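### Section 9.4.2 contradicts itself on the primary NAD+ test: treatment-by-day sits under a p<0.10 reporting rule, is missing from the adjusted model, and no primary model is named

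*Combined protocol and SAP*

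**What the plan says.** Section 9.4.2 sets the null hypothesis as equal rates of NAD+ change from baseline to Day 10 in the two arms. The starting model contains treatment and day. The interaction is to be handled "with the coefficient of the day by treatment interaction term to be added to the unadjusted model".

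The adjusted model is then given by its terms: "Adjusted analyses will be carried out with age, race, clinical site, baseline serum creatinine, treatment and day included in the model". No interaction is in that list. Both models are to be summarized, and neither is called primary.

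The next rule is "A day by treatment interaction term, treatment by day, and treatment by clinical site interactions will be considered and reported and described if found significant", with the threshold p < 0.10. The treatment-by-day term appears in it twice, in different word order.

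Later in the same paragraph the models are said to provide contrasts between arms on the mean rate of change, described as "estimated by the coefficient of day in the model, also known as the slope parameter". They are to be reported as "mean differences in rates of change and 95% confidence intervals and p-values", with no p-value condition.

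On missing data, 9.4.1 prescribes chained-equation multiple imputation of outcomes and covariates, and also relies on maximum likelihood under missing at random. Section 9.4.2 prescribes a cited informative-censoring method, giving dialysis and death as examples.

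For eGFR and proteinuria, 9.4.3 is explicit: "We will focus on the coefficient for the interaction of treatment with time as the primary measure of treatment effect" and "We will consider a p-value <0.05 for this interaction term to indicate a significant treatment effect".

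**The concern.** One coefficient carries the primary efficacy test, and 9.4.2 gives incompatible instructions for it. It is promised unconditionally, it is placed among the interactions reported on a p<0.10 condition, and it is absent from one of the two models that are supposed to deliver it. An analyst has to infer which sentence governs.

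The NAD+ result at p<0.05 is a required element of scenarios 1 and 2 for the follow-on study in section 2.1. Both also require no significant increase in harm, and scenario 1 requires a trend in a secondary outcome. Scenario 3 does not use NAD+. With two models and more than one missing-data approach available, and none designated primary, a choice could be made after the results are seen.

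Section 9.1 adds a smaller mismatch. It words the hypothesis as a difference in mean change to Day 10, which is the same hypothesis as equal slopes only if change is linear in day.

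**Working it through.** **1. The plan's own figures (9.2).** Inputs: 40 per arm, two-sided alpha 0.05, autocorrelation 0.5, difference 42 − 21 = 21 µg/mL, SD 10.
- SD of change = 10 × √(2 × (1 − 0.5)) = 10, so the effect size is 21/10 = 2.1.
- Noncentrality = 2.1 × √(40/2) = 9.39, so power exceeds 99.9%. Reproduced.
- Detectable effect at 80% power = (1.960 + 0.842) × √(2/40) = 0.626, or 0.634 with the noncentral t. Both round to 0.63. Reproduced; the 80% is inferred, because the plan does not state it (90% would give 0.72).

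**2. Which coefficient tests the null.** Write mean NAD+ = b0 + b1·treatment + b2·day + b3·(treatment × day), with treatment = 1 for NR.
- Placebo slope = b2; NR slope = b2 + b3; R_NR − R_Placebo = b3.
- Without b3, the day coefficient is one slope shared by both arms. With b3, it is the placebo slope. In neither case is it a between-arm contrast.

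**3. What the adjusted model returns as listed.** Inputs: the baseline and Day 7 means in section 2.1 (NR 21 to 42, placebo 24 to 21). Straight lines and baseline = Day 1 are assumptions for illustration.
- NR slope = (42 − 21)/6 = 3.50; placebo slope = (21 − 24)/6 = −0.50; difference = 4.00 µg/mL per day.
- Extended over Days 1–10, the mean day is 4.5 days after baseline. NR mean = 21 + 3.50 × 4.5 = 36.75; placebo mean = 24 − 0.50 × 4.5 = 21.75.
- Least squares with treatment and day only: level difference = 36.75 − 21.75 = 15.0; common slope = (3.50 − 0.50)/2 = 1.50.
- Adding the interaction gives day = −0.50 (placebo) and treatment-by-day = 4.00.

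The 4.00 that the null hypothesis concerns is not among the coefficients of the model as listed.

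**4. Cost of not naming a primary model.** Simulation under the null: 20,000 trials, 40 per arm, normal per-subject slopes, five independent covariates. A false positive is counted if either the unadjusted or the adjusted slope test has p<0.05.

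| Slope variance explained by covariates (assumed) | Either test p<0.05 |
|---|---|
| 0% | 6.4% |
| 10% | 6.6% |
| 30% | 7.4% |
| 50% | 8.5% |

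Here the covariates act on the slope. Section 9.4.2 does not mention covariate-by-day terms; 9.4.3 does plan them for eGFR and proteinuria. If covariates enter as main effects only, they are constant within a participant and, with complete daily data, leave treatment-by-day unchanged. A check on the site term with gaps after early discharge (200 simulated trials per correlation structure, 40 per arm, SD 10, site steps of 5 µg/mL) moved the estimate by at most 0.021 per day (compound symmetry) and 0.041 per day (AR(1)). The estimate's SDs were 0.217 and 0.302. The table is therefore an illustration under stated assumptions, not an expected error rate.

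**5. Missing-data passages side by side.** Section 9.4.1 imputes outcomes without naming exceptions. Section 9.4.2 models dropout as informative. Section 9.4.3, for creatinine AUC and for eGFR and proteinuria, classes dialysis, death and withdrawal of consent as informative censoring and applies the method specified for NAD+. That indicates the intent. No sentence says that outcome imputation is set aside for NAD+ or is only a sensitivity analysis.

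**The case against.** The strongest reply is that the paragraph can be read sensibly as a whole. The slope contrasts are promised without a condition and from both models, and 9.4.1 says that treatment-effect estimates and p-values will be tabulated. The unadjusted model is also first listed as treatment and day only, so the adjusted list may be the same shorthand. Endpoint-specific text in 9.4.2 would normally override the general approach in 9.4.1. The trial is a pilot that describes itself as exploratory, and at an effect size of 2.1 the choice of model would hardly change the conclusion.

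Most of this stands as evidence of intent, and it limits the harm. It does not remove the contradiction. The exploratory label in 9.4.1 waives multiplicity correction, not identification of the primary test, and 9.4.3 shows that the needed sentence was within reach.

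A reader might infer more than the documents support:
- *The primary test is run at 10%.* The p<0.10 rule concerns reporting. Sections 2.1, 9.1 and 9.4.1 fix the level at 0.05.
- *The primary contrast would go unreported.* Applied alone, the rule would suppress 90% of null trials (1 − 0.10) and 12.5% at effect size 0.63 (1 − 87.5% power at alpha 0.10, noncentral t, 78 df). The unconditional promise in the same paragraph contradicts that reading.
- *The expected 15% withdrawal means 15 of 100 missing NAD+ series.* Section 7.2 keeps data recorded before withdrawal and continues collection unless consent is withdrawn.

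**Conclusion.** The contradiction is real and should be fixed. As written, 9.4.2 attaches a conditional reporting rule to its own primary coefficient, lists an adjusted model that cannot test the null hypothesis, describes the between-arm contrast by the wrong coefficient, and names no primary model. The outcome imputation in 9.4.1, taken literally, conflicts with the informative-censoring method, although 9.4.3 largely shows which is meant.

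The size is modest. The test level, the stated power and the detectable effect do not change. The quantified risk is a false-positive rate of about 6.4–8.5% instead of 5%. It requires that the analyst take whichever model succeeds, that covariates explain 0–50% of slope variance, and that the adjustment acts on slopes. The documents give no figure for covariate strength. The ambiguity matters more if the true effect is near 0.63 than if it is near 2.1.

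**What to change.** 1. Name one primary NAD+ model, fitted with the informative-censoring method already chosen, containing treatment, day, treatment-by-day and clinical site. Site is the stratification factor; including it is good practice and has little effect on the slope contrast.
2. Carry the 9.4.3 rule over to NAD+: the treatment-by-day coefficient is the primary measure of effect, always reported with its 95% confidence interval and p-value at two-sided 0.05.
3. Add treatment-by-day to the covariate-adjusted model and label that model supportive.
4. Remove treatment-by-day from the p<0.10 list. Leave that rule for treatment-by-site only, with no new threshold for subgroups.
5. Replace the reference to the day coefficient with arm-specific slopes and their difference.
6. State that the 9.4.2 method governs NAD+ missing through dialysis, death or withdrawal. State that multiple imputation of NAD+ is a sensitivity analysis only and is not applied after death.
7. Align 9.1 with the rate-of-change endpoint.

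These are wording changes, with no change to sample size, visits or data collected.

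Reconcile separately the NAD+ sampling schedule after early discharge. Section 9.4.2 says "Whole blood NAD+ will be measured daily in each patient during the first 10 days upon randomization", whereas 8.2 limits daily measurement to the hospital stay, and 6.1.1 and 8.1 provide one Day 10 blood collection after discharge.
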